3.1. Study Objectives

3.1.1. Primary Objective

The primary objective of this study is to confirm that Panzyga is superior to placebo (0.9% w/v sodium chloride) for reducing the severity of symptoms associated with PANS in pediatric patients.

3.1.2. Secondary Objectives

The secondary objectives of this study are

- to verify the sustainability of the reduction of the severity of symptoms in pediatric patients treated with Panzyga, and
- to assess the efficacy of Panzyga treatment in reducing functional impairment associated with PANS.

3.1.3. Exploratory Objectives:

The exploratory objectives of this study are to:

- assess the safety parameters of Panzyga administration
- characterize the pharmacokinetic (PK) exposure and the fluctuation thereof throughout the treatment course

Additional exploratory objectives of this study are to:

- assess the correlation between CGI-I and CY-BOCS
- assess the PANS improvement in pediatric patients

3.2. Study Endpoints (Target Variables)

This section defines the target variables collected or derived for the evaluation of the endpoints; please refer to sections 8 to 12 for analysis details.

3.2.1. Primary Target Variables

The primary endpoint is defined as:

Improvement of neuropsychiatric symptomatology and behavior in PANS patients determined by clinician-rated CY-BOCS score. The mean changes in the total CY-BOCS score from Baseline to Week 9 will be compared between Panzyga and Placebo treatment groups to demonstrate superiority.

The primary target variable to assess impairments associated with PANS symptoms is thus the clinician-rated CY-BOCS score.

The total CY-BOCS score is the sum of items 1 -10 of the assessment form; each of the item's score is an integer between 0 and 4. Consequently the total CY-BOCS score ranges between 0 (no impairment) to 40 (maximum impairment). For participation in the study, patients must have a total CY-BOCS score of at least 16 based on specific criteria defined in the protocol.

3.2.2. Secondary Target Variables

Efficacy:

CY-BOCS score at the end of the follow-up period at Week 18 will be compared to the Week 9 scores within the (Panzyga – Placebo) treatment group to assess the durability of the clinical benefit associated with Panzyga treatment.

The protocol specifies the following standardized instruments for the assessment of behavioral changes as secondary efficacy endpoints:

- Clinical Global Impression (CGI) – For the confirmatory endpoint analysis the CGI-I (CGI – Improvement) total score will be used
- Parent & Child OC Impact Scale – Revised (COIS-RP and COIS-RC) – For the confirmatory endpoint analysis the COIS-RP total score will be used
- The Swanson, Nolan, and Pelham Rating Scale (SNAP-IV, 26 item)
- Parent Tic Questionnaire (PTQ)

These scores are therefore considered as secondary target variables; please refer to the protocol for details on these instruments.

3.2.3. Exploratory Target Variables

- Columbia Suicide Severity Rating Scale (C-SSRS) for the prospective assessment of suicidality
- All adverse events (AEs) throughout the study period, with particular emphasis on thromboembolic events (TEEs) and hemolytic transfusion reactions (HTRs).
- Vital signs (blood pressure, heart rate, body temperature and respiratory rate).
- Physical examinations
- Laboratory parameters (hematology, clinical chemistry)
- Total IgG plasma levels for pharmacokinetic assessments

Additional exploratory target variables are:

- Correlation between change in CY-BOCS from baseline to Week 9 and CGI-I assessment at Week 9
Note: the change in CY-BOCS will be measured by ratio of the CYBOCS at Week 9 to that at Baseline.
- Correlation between change in CY-BOCS from Week 9 to Week 18 and CGI-I assessment at Week 18
- The percentage (%) of pediatric patients with PANS improvement at Week 9 and Week 18.

PANS improvement will be defined as improvement of PANS symptoms based on CGI-I ratings at Week 9 since Week 3, and at Week 18 since Week 12. Patient will be evaluated as PANS improvement if the CGI-I score is 3 (Minimally Improved) or better at the evaluated visit.

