##### 3.1.3 Exploratory Endpoints

- All AEs throughout the study period, with particular emphasis on TEEs and HTRs.
- Vital signs (blood pressure, heart rate, body temperature and respiratory rate).
- Physical examination at Baseline, and targeted physical examinations at Week 3, Week 6, Week 9/Early Termination Visits.
- Laboratory parameters (hematology, clinical chemistry) at Baseline and Week 9/Early Termination Visits.
- Columbia Suicide Severity Rating Scale (C-SSRS)
- Pharmacokinetic parameters related to IgG sampling (Table 3):
  - Prior to start of the first infusion of each of the three infusion cycles, i.e. three trough levels per patient in all patients
  - 10 to 60 minutes after the end of the last infusion cycle in all patients
  - In the PK-subset (first six enrolled patients), in addition to the samples above, the following three samples were collected:
    - (i) a trough sample prior to the second infusion of the first cycle;
    - (ii) a sample within 10 to 60 minutes after the end of the first infusion of the first cycle;

- (iii) a sample within 10 to 60 minutes after the end of the second infusion of the first cycle
- Correlations between change in CY-BOCS from baseline to Week 9 (from Week 9 to Week 18) and CGI-I assessments at Week 9 (Week 18)
- Percentage of pediatric patients with PANS improvement at Week 9 and Week 18. For this analysis, PANS improvement is defined as a CGI-I rating of 1 (Very much Improved), 2 (Much improved), or 3 (Minimally Improved).

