The **CGI** rating scales are commonly used measures of symptom severity, treatment response and the efficacy of treatments in clinical trials of patients with mental disorders. The Clinical Global Impression - Severity scale (CGI-S) is a 7-point scale that requires the clinician to rate the severity of the patient's illness at the time of assessment, relative to the clinician's past experience with patients who have the same diagnosis. Considering total clinical experience,

a patient is assessed on severity of mental illness at the time of rating 1 = normal; not at all ill; 2, borderline mentally ill; 3, mildly ill; 4, moderately ill; 5, markedly ill; 6, severely ill; or 7, extremely ill. The Clinical Global Impression - Improvement scale (CGI-I) is a 7-point scale that requires the clinician to assess how much the patient's illness has improved or worsened relative to a baseline state at the beginning of the intervention and is rated as: 1, very much improved; 2, much improved; 3, minimally improved; 4, no change; 5, minimally worse; 6, much worse; or 7, very much worse [45]. Telemedicine platforms such as video/phone can be utilized.

A specific and commonly used measure of OCD-related impairment is the COIS-R [46], which is a revision of the original **COIS** and is available in parallel parent- and child-report versions, assessing impairment due to OCD across multiple functional domains [47]. The Child Obsessive-Compulsive Impact Scale-Revised consists of parallel 33-item parent and child-report versions assessing impairment due to OCD across multiple functional domains (parent-report: Daily Living Skills, Family, Social, School; child-report: School, Social, Activities). Items are rated on a 4-point scale from 0 (not at all) to 3 (very much) [46]. The parent and child versions of the COIS-R exhibit good to excellent internal consistency and acceptable to good test-retest reliability across subscales [48]. The parent-report version has demonstrated sensitivity as a predictor of treatment response, while the child-report version is sensitive to treatment response for both cognitive behavioral therapy (CBT) and medication [48]. Telemedicine platforms such as video/phone can be utilized.

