10.3.2. Correlation between CY-BOCS and CGI-I

The correlation analysis between CY-BOC and CGI-I will be performed based on ITT Population for the following exploratory endpoints:

- [REDACTED]
- [REDACTED]
- [REDACTED]
- [REDACTED]

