10.3.3. Pediatric Patients with PANs improvement

PANS improvement will be defined as improvement of PANS symptoms based on CGI-I ratings at Week 9 since Week 3, and at Week 18 since Week 12. Patient will be evaluated as PANS improvement if the CGI-I score is 3 (Minimally Improved) or better at the evaluated visit.

The descriptive statistics (n and percentage %) for patients with PANS improvement will be summarized by treatment groups at Week 9 and Week 18.

not

11. Safety and Tolerability Analyses

The safety analysis will comprise descriptive statistics, tabulations and listings of all adverse events (AEs), safety laboratory results, and physical examination findings. The safety analysis will be made with the FAS, including all randomized patients who received at least part of one infusion of Panzyga or placebo. In the event that a patient received the wrong study drug (i.e. did not take the randomized study drug), the actual treatment will be used for safety analyses.

To account for the cross-over follow-up phase in this study, safety tabulations will differentiate between 3 patients groups according to their treatment status as defined in section 8.4 above.

In particular, AEs in patients with treatment sequence (Panzyga – Placebo) that start more than 21 days after the last administration of Panzyga will be reported separately, and an additional medical review will be performed to identify any possible signal of events with long latency.

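### Does the SAP's mention of Weeks 3 and 12 change who counts as improved on CGI-I?

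*SAP*

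**What the plan says.** Protocol 3.1.3 lists the percentage of patients with PANS improvement at Weeks 9 and 18 as an exploratory endpoint: "For this analysis, PANS improvement is defined as a CGI-I rating of 1 (Very much Improved), 2 (Much improved), or 3 (Minimally Improved"). It names no comparison visit. The reference state comes from the scale description in protocol 3.3.3, where the clinician judges how far the illness has "improved or worsened relative to a baseline state at the beginning of the intervention".

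SAP 3.2.3 describes the same endpoint differently: "PANS improvement will be defined as improvement of PANS symptoms based on CGI-I ratings at Week 9 since Week 3". SAP 10.3.3 repeats the definition, with the second-phase reference, as "CGI-I ratings at Week 9 since Week 3, and at Week 18 since Week 12". In both sections the counting rule follows at once: "Patient will be evaluated as PANS improvement if the CGI-I score is 3 (Minimally Improved) or better at the evaluated visit". SAP 10.3.3 plans only counts and percentages by treatment group.

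SAP 3.2.3 also plans two exploratory correlations. One pairs the Baseline-to-Week 9 change in CY-BOCS with CGI-I at Week 9, with the note that "the change in CY-BOCS will be measured by ratio of the CYBOCS at Week 9 to that at Baseline". The other is the "Correlation between change in CY-BOCS from Week 9 to Week 18 and CGI-I assessment at Week 18". SAP 10.3.2 begins by stating that "The correlation analysis between CY-BOC and CGI-I will be performed based on ITT Population"; the bullets that follow are redacted.

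**The concern.** Weeks 3 and 12 each fall one cycle after a phase begins. If they are comparison points, the SAP's improvement covers only the last six weeks of each nine-week phase, while the protocol's covers the whole of it. A patient who responds to the first cycle and then holds that gain would be improved against Baseline but unchanged against Week 3. A reader of the results could then misunderstand what the percentage measures.

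The second phase adds a further doubt. The visible text does not say whether the start of the intervention means Week 0 or the crossover at Week 9. If raters kept Week 0 as the reference, the Week 18 correlation would set a nine-week CY-BOCS change against an 18-week global rating. A modest coefficient could then reflect the unequal intervals rather than poor agreement between the scales.

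**Working it through.** The plan gives no figure to reproduce, so the check compares the rules and the lengths of the intervals.

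**1. The counting rule.** Let G be the CGI-I score recorded at the evaluated visit, an integer from 1 to 7 (protocol 3.3.3).

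- Protocol 3.1.3: improved if G is 1, 2 or 3.
- SAP 3.2.3 and 10.3.3: improved if G is 3 or better, that is, G ≤ 3.

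On this scale the two conditions are the same. Neither contains a Week 3 or Week 12 score, and no difference between visits is formed. For any set of recorded ratings the two documents return the same percentage.

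**2. What fixes the reference state.** The rater applies it when scoring. Protocol 3.3.3 defines it, and SAP 8.4 leaves scoring of the instruments to their manuals. A phrase in the SAP's description of an exploratory endpoint does not alter a score already recorded.

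**3. Interval lengths under each possible reference.**

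| Evaluated visit | Reference | Interval |
|---|---|---|
| Week 9 | Week 0 | 9 − 0 = 9 weeks |
| Week 9 | Week 3 | 9 − 3 = 6 weeks |
| Week 18 | Week 0 | 18 − 0 = 18 weeks |
| Week 18 | Week 9 | 18 − 9 = 9 weeks |
| Week 18 | Week 12 | 18 − 12 = 6 weeks |

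These would be different quantities if raters used different references. The protocol's scale definition excludes Weeks 3 and 12, because no intervention begins there. They are, however, the first scheduled visits after dosing starts in each phase (protocol Study Outline, Study Procedures). The phrase may therefore mean only that ratings are collected from those visits onward, and on that reading there is no conflict.

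**4. The Week 18 correlation.** The CY-BOCS change runs from Week 9 to Week 18, nine weeks. In a crossover with no wash-out (SAP 4.1) the second intervention begins at Week 9, so protocol 3.3.3 can be read as anchoring the second-phase CGI-I there. The rating then also covers nine weeks and the pairing is consistent. This mirrors the first correlation, where both quantities run from Week 0 to Week 9. By the same parallel, the ratio for the second phase would be Week 18 over Week 9. The places where an anchor or a second ratio would be written (the SAP 10.3.2 bullets, protocol 6.1 and the flow charts) are redacted, so their absence from the visible text does not show a gap in the plan.

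**The case for a change.** The strongest case is that the SAP contradicts itself in plain sight. Within SAP 3.2.3, the Week 9 CGI-I is paired with change since Baseline for the correlation and then described by reference to Week 3; the Week 18 rating is paired with change since Week 9 and then described by reference to Week 12. The wording appears in two sections, and the protocol and SAP 5.0 both carry the date 21 July 2023, so it is not superseded text. The ordinary sense of the words is a comparison with Week 3. The protocol's rule on worsening symptoms (section 4.3.2) adds another time reference for CGI-I, the previous visit.

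The possible effect on the correlation can also be illustrated. Suppose the Week 18 CGI-I tracked CY-BOCS change since Baseline perfectly, with equal variances σ² and a common correlation r across Weeks 0, 9 and 18. The covariance of the two changes is σ²(1 − r) and each variance is 2σ²(1 − r), so the correlation is 1/2 = 0.50, against 1.0 with matched intervals.

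Part of this stands. The phrase is loose, and the meaning of the Week 18 percentage depends on the rater's reference: a Panzyga–Placebo patient who holds a first-phase gain is improved against Week 0 and unchanged against Week 9. A table footnote should state the reference used. The rest does not carry. The counting rule does not use the phrase. The 0.50 rests wholly on assumed inputs, including the Week 0 anchor; with a Week 9 anchor there is no attenuation from this source. The two complaints also pull against each other: if the phrase does set a reference, the SAP states one for the second phase; if it does not, the conflict with the protocol disappears.

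**Conclusion.** No change to the plan is called for. The size of the effect on the calculated improvement percentage is zero, because both documents apply the same cut-off to the same recorded score; only the description is ambiguous. An interval mismatch in the Week 18 correlation is possible but not shown, and no attenuation figure can be attached to this trial from the documents.

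This rests on two assumptions: that raters followed the scale definition in protocol 3.3.3, and that the analyst takes the second-phase reference from the rater instructions when labelling the Week 18 outputs. Both are ordinary practice. The primary CY-BOCS analysis does not use this definition, and SAP 4.1 limits the secondary CGI-I analysis to data up to Week 9. Amending either document would tidy a sentence about exploratory outputs without altering a result.

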3.2.4. Important Covariates and Patient Characteristics

The following variables have been identified as important patient characteristics and will be used for stratification as detailed in section 4.3:

[REDACTED]	[REDACTED]	[REDACTED]
[REDACTED]	[REDACTED]	[REDACTED]
[REDACTED]	[REDACTED]	[REDACTED]

[REDACTED]	[REDACTED]	[REDACTED]	[REDACTED]
------------	------------	------------	------------

Additionally, the effect of the following variables on the endpoints will be assessed in an exploratory manner:

- Age: considered as continuous variable and to define the following subgroups:
 - Children (6 to 12 years) and Adolescents (13 to 17 years) (predefined)
 - < median age and ≥ median age for possible population enrichment (interim data)
- Sex
- Onset of PANS symptoms:
 - “< 6 months”: Onset of initial symptoms within 6 months prior to screening
 - “≥ 6 months”: Patients with relapsing symptoms: initial symptoms may not have been more than 12 months prior to the screening and must have fully resolved, their recurrence must be within 6 months prior to screening
- Baseline CY-BOCS score: considered as continuous variable and to define 2 subgroups:
 - Moderate (16 to <24) and Severe (≥24)

Property of Octapharma. Do not copy or distribute without written permission.

4. Study Methods

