#### 4.1.1 Inclusion Criteria

Patients who meet all of the following criteria are eligible for the study:

1. Patients  $\geq 6$  to  $\leq 17$  years of age.
2. Confirmed diagnosis of moderate to severe PANS with prominent and stable OCD symptoms (i.e. CGI—Severity-OCD rating of  $\geq 4$  or higher on 2 ratings without a change of more than 1 unit between measurements) based on the following criteria [1]:
  - a. Abrupt dramatic onset of OCD meeting DSM-5 diagnostic criteria for OCD as confirmed by the MINI-KID-7
  - b. Concurrent presence of additional neuropsychiatric symptoms, with similarly severe and acute onset, from at least two of the following seven categories, that are not better explained by a known neurologic or medical disorder, such as SC, systemic lupus erythematosus, Tourette disorder, or other:
    - i. Anxiety (particularly, separation anxiety)
    - ii. Emotional lability (extreme mood swings) and/or depression
    - iii. Irritability, aggression and/or severely oppositional behaviors
    - iv. Behavioral (developmental) regression (examples, talking baby talk, throwing temper tantrums, etc.)
    - v. Deterioration in school performance
    - vi. Sensory or motor abnormalities

- vii. Somatic signs and symptoms, including sleep disturbances, bedwetting or urinary frequency
3. Signed informed consent of patient's legal representative(s)/guardians(s). If patients are old enough to understand the risks and benefits of the study (as determined by each institution), they should provide written assent/consent.
4. Legal representative(s)/guardians(s) must be capable of understanding and complying with the relevant aspects of the study protocol.

Patients who will additionally meet the following optional inclusion criteria will be identified as PANDAS patients:

1. An episodic (relapsing-remitting) course of symptom severity.
2. Temporal association between symptoms onset or exacerbation and GAS infections (positive throat culture and/or anti-GAS antibody titers).

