#### **4.1.2 Exclusion Criteria**

Patients who meet any of the following criteria are not eligible for the study:

1. Onset of current PANS episode more than 12 months prior to first IMP treatment.
2. a. In patients with relapsing episodes: Onset of initial PANS episode more than 24 months prior to first IMP treatment  
b. In patients with relapsing episodes: Absence of significant improvement and stabilization between the episodes according to investigator's judgment.
3. Contraindications to receiving IVIG, including:
  - a. History of severe hypersensitivity, e.g. anaphylaxis or severe systemic response, to immunoglobulin, blood or plasma-derived products, or any component of Panzyga.
  - b. IgA deficiency with antibodies to IgA (<7 mg/dL).
  - c. Hyperviscosity syndromes or known or suspected hypercoagulable conditions as inferred from clinical history, which can increase risks of thrombosis associated with IVIG administration.
  - d. History of arterial or venous thrombotic or TEEs within the last year prior to Baseline. History of acquired or inherited thrombophilia any time prior to Baseline.
  - e. Need for live virus vaccine within three months after receiving study drug.
  - f. Renal dysfunction (creatinine > 120 µmol/L or 1.36 mg/dL), history of renal dysfunction, or known risk factor for renal dysfunction (chronic renal insufficiency, diabetes mellitus, taking known nephrotoxic medication). For Italy, estimated glomerular filtration rate (eGFR) needs to be calculated with the 2009 Schwartz equation (eGFR = k \* height/Serum creatinine (SCr), where k is 0.413) [2]. eGFR must not be below 30.

4. Severely restricted food intake likely to require parenteral nutrition, and <5th percentile BMI-for-age (BMI Percentile Calculator for Child and Teen based on Centers for Disease Control and Prevention growth charts for children and teens ages 2 through 19 years).
5. Body mass index  $\geq 40 \text{ kg/m}^2$ .
6. Presence of symptoms consistent with autism or schizophrenia, bipolar disorder, or other psychotic disorder (unless psychotic symptoms have onset coincident with PANS).
7. Presence of serious or unstable medical illness, psychiatric (e.g. high suicide risk) or behavioral symptoms that would make participation unsafe or study procedures too difficult to tolerate.
8. Treatment with systemic corticosteroids within eight weeks before randomization.
9. Treatment with NSAIDs within five days before randomization.

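### The SAP cites a CY-BOCS ≥16 entry rule that is not in the protocol's eligibility criteria, and its onset and severity subgroups leave some eligible patients unclassified

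*SAP*

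**What the plan says.** **Entry.** SAP 3.2.1 states: "For participation in the study, patients must have a total CY-BOCS score of at least 16 based on specific criteria defined in the protocol". Protocol 4.1.1 sets severity at entry by a CGI-Severity-OCD rating of 4 "or higher on 2 ratings without a change of more than 1 unit between measurements". No CY-BOCS threshold appears in 4.1.1, in 4.1.2 or in the matching lists of the Study Outline. SAP 4.2 gives none either and refers to the protocol for the full list.

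**Onset.** Protocol 4.1.2 excludes "Onset of current PANS episode more than 12 months prior to first IMP treatment". For relapsing patients it also excludes "Onset of initial PANS episode more than 24 months prior to first IMP treatment" and "Absence of significant improvement and stabilization between the episodes". SAP 3.2.4 defines two onset subgroups. The one labelled <6 months is "Onset of initial symptoms within 6 months prior to screening". The one labelled ≥6 months is described as "Patients with relapsing symptoms: initial symptoms may not have been more than 12 months prior to the screening and must have fully resolved", and "their recurrence must be within 6 months prior to screening".

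**Severity.** SAP 3.2.4 uses baseline CY-BOCS as a continuous variable and also in two bands, 16 to <24 and ≥24.

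**Version.** The SAP preface names protocol Version 3.0 of 25 January 2021 as the one reviewed. The protocol supplied is dated 21 July 2023.

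**The concern.** The SAP attributes to the protocol an entry rule that the protocol's eligibility criteria do not contain. Its text under the ≥6-month label is worded as an entry restriction, and it is narrower than the protocol's actual limits. A subgroup rule narrower than eligibility drops eligible patients from the analysis or leaves the programmer to decide where they go.

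Two things are at stake. The first is the pre-specified exploratory assessment of onset and baseline severity. The second is the per-protocol set. SAP 7 lists entry-criteria violations first among the deviations to be considered for exclusion, and the primary and secondary efficacy analyses are repeated on that set. Someone working from SAP 3.2.1 would call a baseline score below 16 a violation; someone working from Protocol 4.1.1 would not.

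**Working it through.** No stated figure needs reproducing; this is a check of definitions.

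**Notation.** F is initial onset and R is onset of the current episode, both in months before screening. For a single episode, F = R; for a relapsing patient, R < F. The protocol counts back from first IMP and the SAP from screening. Let s be the time from screening to first IMP. Assuming first IMP is given at randomization, s runs from 0 to 28 days, and 28 / 30.4375 = 0.92 month.

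**Protocol 4.1.2 (eligible).** R ≤ 12 − s. Relapsing patients also need F ≤ 24 − s and significant improvement with stabilization between episodes.

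**SAP 3.2.4 (label and text both applied).**
- <6 months: F < 6.
- ≥6 months: relapsing, 6 ≤ F ≤ 12, R within 6, earlier episode fully resolved.

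**Who is left out.** An unclassified patient must have F ≥ 6, since otherwise the first group takes them. A single-episode patient with F ≥ 6 cannot enter the second group. A relapsing patient with F ≥ 6 misses it only by failing at least one of its three remaining conditions. The unclassified patients are therefore exactly these four types, which can overlap:

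| Type | Eligible profile | Example |
|---|---|---|
| 1 | Single episode, 6 to 12 − s months old | onset 9 months ago |
| 2 | Relapsing, first onset 12 to 24 − s months ago | first 18, current 3, fully resolved between |
| 3 | Relapsing, current episode more than 6 months old | first 11, current 8, fully resolved between |
| 4 | Relapsing, F ≥ 6, earlier episode improved but not fully resolved | first 10, current 3 |

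Each example stays eligible with s = 0.92. Enumerating onset profiles on a grid at s = 0 and s = 0.92 gave the same four types and no others. The grid tests logic only and says nothing about patient shares.

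**Width of the gaps.**
- Single episode: (12 − s) − 6 = 6.0 months at s = 0, and 12 − 0.92 − 6 = 5.08 at s = 0.92.
- Relapsing, first onset: (24 − s) − 12 = 12.0 months at s = 0, and 24 − 0.92 − 12 = 11.08 at s = 0.92.

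The different anchor dates shift the gaps by at most 0.92 month, so they are not the cause.

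**Severity.** The scale runs from 0 to 40. Scores of 0 to 15 fall in neither band, and no listed eligibility criterion excludes them.

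**Check of the proposed split (F < 6 versus F ≥ 6).** It covers every F once, so nobody is unclassified. Every patient the SAP already places keeps the same label, because its ≥6 group already has F ≥ 6. Splitting on R instead would not do this: the SAP's ≥6 group requires R within 6 months, so those patients would move to the <6 side.

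**The case against.** The strongest reply is that the labels govern. Under <6 and ≥6 months alone, everyone is classified, and the sentence under the second label is simply a leftover restatement of entry limits. That is plausible, and the labels would indeed be exhaustive. But label and description then give different answers for the four types, and the SAP does not say which one controls. Taking the description alone does not help either. It has no 6-month lower bound on first onset, so a relapsing patient with first onset at 5 months, full resolution and recurrence at 2 months would meet both descriptions.

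Second, the consequences are small. This stands in large part. SAP 3.2.4 calls these assessments exploratory, baseline CY-BOCS is also used as a continuous variable, and efficacy analyses are primarily ITT. SAP 8.4 lets minor derivations be documented in programs, and SAP 7 limits per-protocol exclusions to important deviations classified before lock or unblinding. These provisions contain the problem; they do not correct a rule that is wrong as written.

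Third, dropping the relapse and resolution conditions pools single continuous episodes with recent relapses. That is true, but it is what a label based on time since initial onset implies.

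Fourth, the SAP's version history says the current version was updated for protocol Versions 5.0 and 6.0, so the preface line may be one stale reference. That is fair, but it does not change the text of 3.2.1 or 3.2.4.

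**Conclusion.** The point holds. The ≥16 rule is absent from the protocol's eligibility criteria, which are not redacted. The visit procedures and flow charts are redacted, so a mention there cannot be excluded, but it would not be among the eligibility criteria. Four kinds of eligible patient fit no onset subgroup when label and text are both applied, and any eligible patient with a baseline CY-BOCS below 16 fits no severity band.

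The number of patients affected cannot be derived: the documents give no frequencies, and scores below 16 may be few given the CGI-Severity requirement. The gap widths are calendar spans, not patient shares, and assume first IMP at randomization. The visible effect is confined to exploratory subgroups and an avoidable ambiguity for the per-protocol review. The list of interim enrichment subgroups is redacted, so no effect on enrichment is claimed. Carry-over from an earlier protocol version may explain the wording, but Version 3.0 is not available to check.

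**What to change.** - Reconcile the ≥16 sentence in SAP 3.2.1 with Protocol 4.1.1 and 4.1.2; if those criteria stand, delete it.
- In SAP 3.2.4, keep the onset labels and define them as initial PANS onset <6 versus ≥6 months before screening. Remove the relapse, 12-month, full-resolution and recurrence conditions.
- Define severity as baseline CY-BOCS <24 versus ≥24. This is exhaustive whether or not a floor of 16 is confirmed; with a floor, the lower group is the existing 16 to <24 band.
- Use the same definitions wherever these subgroups appear, and update the protocol version in the SAP preface.

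The cost is SAP wording and derivation code. No new data are needed, and the change should be made before database lock.
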